#### 5. STUDY INTERVENTIONS

### 5.1 Interventions, Administration, and Duration

The app is a non-Significant Risk Device (NSR). It does not perform diagnostic tasks or tie in with a device that requires FDA clearance (such as apps aiding in ECG interpretation or detection of skin malignancies). Review of the Human Subjects component by the NIH for this grant proposal resulted in "Human Subjects: Certified, No concerns" in the Summary Statement.

Group	Intervention
Experimental	Electronic Tablet Comfort Talk® appRv2
Control	Electronic Tablet White Noise

Patients will be given a tablet containing either the app or white noise control content during their clinic visit. App patients will receive a download coupon for the app before they leave home and are at liberty to download the app at home to their own devices. The clinic visit usually last approximately 45 min during which the participant can listen to the app or white noise as little or much as he or she desires.

## 5.2 Handling of Study Interventions

The study site will receive 4 tablets labeled A,B,C,D without knowledge which tablet contains the app and which contains white noise.

#### 5.3 Concomitant Interventions

n/a

#### 5.3.1 Allowed Interventions

n/a

#### 5.3.2 Required Interventions

n/a

#### 5.3.3 Prohibited Interventions

n/a.

#### 5.4 Adherence Assessment

Throughout the project we have and will continue to use the agile approach of Behavior-Driven-Development (BDD) to design and implement features that research suggests to be effective (1)( http://www.bdd-in-action.com/). This has been achieved for the prototype which is functioning according to spec. Design supports data-mining capability of anonymized selection preferences and feedback. Technical performance and good development practices were insured through review of code and test results by qualified software engineers, and the app stores review and approval process.

In accordance with BDD, testing will be continued during the clinical pilot trial to assess technical performance in the hands of patients. App usage patterns in clinic will be established electronically through background capture of usage data and upload to the database server. This data allows analysis of variables such as options chosen, audio segments played and time spent listening to each segment and in total.

A criterion of success will be that 90% of patients in app group listen to app  $\geq$ 5 min. This will be a summary result based on the cohort of all app patients and not allow identification of individual patients.

#### 6. STUDY PROCEDURES

The schedule of evaluations and events is shown on the following page and listed in the CRF form in Appendix 15.

## 6.1 Schedule of Evaluations

Appointment Procedures	Visit 1	After Visit 1 (upon returning diary)
Study Consent/Assent	Х	
Demographics	Х	
Medical History	Х	
Evaluate eligibility and withdrawal criteria	Х	
Randomization	Х	
NIDA Quick Screen	Х	
Pre-Intervention Pain/Anxiety	Х	
Scales		
Tablet Intervention	Х	
Intervention Pain/Anxiety Scales	Х	
Diary Distribution	X	
Satisfaction Survey	X	
Diary Return (via mail)		Х
Check Distribution (via mail)		X
Coupon Distribution (test group)	Х	
Coupon Distribution (control group)		X

## 6.2 Description of Evaluations

## 6.2.1 Screening Evaluation

## **Consenting Procedure**

The study team will review the Craniofacial Pain Center schedule to identify patients that are at least 18 years of age with an upcoming visit. Potential subjects will be contacted via phone by a research team member prior to their upcoming visit to introduce the study, using an IRB-approved phone script. If the patient is interested in participating in the study, they will be asked to come into the clinic half an hour before their scheduled appointment. This half hour will be used to consent the participant, and complete randomization.

Patients who present at the Craniofacial Pain Center may also be approached by a member of the research team, and asked for their interest to participate.

All of the forms of recruitment have been submitted to the Tufts IRB and been approved. The screening interview/questionnaire or screening script will be used for recruitment. They do not require separate consent. There will be a single consent form.

The site PI and research assistant will perform the consent procedure.

Patients' level of education will not be an eligibility prerequisite. To be eligible to participate, patients need the cognitive ability, through whichever education acquired, to write and read in English, as the ComfortTalk scripts, study scales and take-home diary are in English and to be able to operate a standard smart tablet or smart phone.

The protocol and consent forms are reviewed on annual basis through the Tufts IRB. Should the need for changes become necessary they will be handled through the Tufts' IRB after prior review by NCCIH.

All study records, including assent forms will be kept in locked cabinets at the Tufts Dental School in a room that has limited access and remains locked at all times. Once the study is terminated, all study records will be kept in locked cabinets or will be sent to Iron Mountain (a contracted secure off site facility) at the end of the study. They will be maintained for a minimum of 7 years.

Data entry quality reports, including availability of signed consent forms, will be prepared by an outside quality monitor every 4 months and submitted to Hypnalegsics, LLC, as described in the DSMP. The first report will be obtained early during the enrollment Phase (month 1-3), and if satisfactory with regard to quality, obtained again 4 months later or after the last patient has been enrolled, whichever occurs earlier. Should there be concerns an earlier follow-up visit will be done.

#### **Screening**

There are no specific screening tests or evaluations. Patients will be asked to come 30 min prior to their routine clinic appointment to enable the consent and confirm eligibility criteria:

- Male or female patients age 18 years and older
- Scheduled to undergo a dental procedure at the Craniofacial Pain Center
- Able to hear, write and read in English, as the ComfortTalk scripts, study scales and take-home diary are in English
- Able to operate a standard smart tablet or smart phone and have access to a smart tablet, smart phone at home, or computer-based app download
- Willing and able to give informed consent

#### 6.2.2 Enrollment, Baseline, and/or Randomization

#### **Enrollment**

There is a single informed consent form. Enrollment is defined as the randomization date and is recorded on the case report form.

#### **Baseline Assessments**

Once the patient is enrolled *Demographics* and *History* will be recorded on the Tufts University School of Dental Medicine Research Participant& Dental History form (Appendix).

Assessments include:

- Age
- Gender
- Race
- Medical history
- Medications

*Eligibility and withdrawal criteria* will be rechecked prior to randomization by going through the CRF form.

The participant will be asked to complete a *NIDA Quick Screen*. No identifiable information will be collected on the NIDA Quick Screen (only the subject ID number). The NIDA (National Institute on Drug Abuse) Quick Screen will be used to assess drug use (including tobacco, alcohol and illegal substances) and nonmedical use of prescription drugs. The NIDA Quick Screen is a brief questionnaire that addresses overall substance use risk, with likely utility for use in a dental setting. This screening tool is intended to be used by doctors serving adult patients in general medical settings. Its algorithm also identifies patients in need of counseling. The instrument is not used as legal-criminal screen. Furthermore, the NIDA is expected to be a routine tool for the history intake at the Craniofacial Pain Center as an important clinical tool in patient assessment.

The information collected via the NIDA quick screen will be compared to post-visit self-reported medication data from the diary, in order to evaluate any changes in opioid use after their dental visits

The participant will then be verbally asked to indicate his/her *anxiety and pain levels* on validated 0-10 scales (0-no pain/anxiety at all, 10-worst pain/anxiety possible). The research assistant will ask about their pain and anxiety using the same verbiage provided on the patient diary, and record their response.

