#### 4. SELECTION AND ENROLLMENT OF PARTICIPANTS

## 4.1 Inclusion Criteria

- Male or female patients age 18 years and older
- Scheduled to undergo a dental procedure at the Craniofacial Pain Center
- Able to hear, write and read in English, as the ComfortTalk® scripts, study scales and take-home diary are in English
- Able to operate a standard smart tablet or smart phone and have access to a smart tablet, smart phone at home, or computer-based app download
- Willing and able to give informed consent

Contraception will not be necessary for participation in the trial.

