#### 9.5.2 Secondary Outcomes

With regard to Phase I of the trial feasibility parameters will be

- number of enrolled patients by day 150 after initiation of recruitment in the clinic (=day 1)
- number of returned packages of filled out diary cards.
- percentage of patients in app group listen to app ≥5 min

With regard to Phase I

- anxiety on a validated 0-10 scale in the dental waiting room
- pain on a validated 0-10 scale in the dental waiting room
- anxiety q10 min (+/- 2 mins) on during dental treatment
- pain q10 min (+/- 2 mins) during dental treatment
- anxiety, average, and maximal anxiety for 7 days after treatment
- pain, average and maximal pain for 7 days after treatment
- use of prescription and nonprescription drugs for 7 days after treatment
- patient satisfaction

•

Pain and anxiety will be measured on 0-10 verbal self-reporting scales (0=no pain/anxiety at all, and 10=worst pain possible). The pain scale is recommended standard in the NIH Toolbox (62). For the 0-10 anxiety scale we previously demonstrated convergent and discriminant validity (63).

Anxiety and pain measures will obtained using these scales by verbally asking the patient "How is your Comfort Level on a scale with 0-no anxiety at all, and 10 worst anxiety possible and 0=no pain at all and 10=worst pain possible":

- At the beginning of the waiting room time after consent
- At the end of the waiting room time
- After the patient enters the dental treatment room and sits down = time 0 of chair time
- Every 10 minutes (+/- 2 minutes) thereafter while on the chair
- When leaving the dental treatment room

Once returned home the patients are asked to use the same scales to write down on daily diary cards for 7 days before bedtime as follows:

PLEASE INDICATE YOUR COMFORT LEVELS WITH A NUMBER BETWEEN 0 and 10

With regard to pain (0=no pain at all and 10=worst pain possible)

- Right now:
- On the average today:
- At its maximum today:

With regard to anxiety (0=no anxiety at all and 10=worst anxiety possible)

- Right now:
- On the average today:
- At its maximum today:

Patient Satisfaction will be assessed using a modified Press Ganey Outpatient Survey template (64) adjusted to dental care and supplemented with a question regarding helpfulness of the app on the same 5-point scale as the remainder of the survey. The Press Ganey instrument has been found to possess suitable psychometric properties for outpatient medical practice survey (65).

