If the data does not meet the assumptions required for the time-series analysis methods listed above, the time-series data from each patient will be summarized by calculating area under the curve using trapezoidal rule. Normality will be assessed graphically using histograms and q-q plots. Area under the curve will be compared between the two treatment groups using t-test if normally distributed or if normality can be achieved by log-transformation. Mann-Whitney U test will be used if data is non-normal.

Pain and anxiety for the week after the post procedure will be assessed for linearity graphically. Individual patient pain and anxiety slopes will be compared using t-test or Mann-Whitney U test, as appropriate, to determine if the rate of change of pain and anxiety is different between treatment and control groups. In addition, the overall mean pain and mean anxiety for each patient will be calculated and compared between treatment and control groups using t-test or Mann-Whitney U test as appropriate.

Drug usage, converted in equivalence drug score, and satisfaction scores will be assessed by t-test if normally distributed or Mann-Whitney-U test if non-normal.

All tests will be two-sided at a significance level of <0.05. Sample size will be based on results of Phase I assuming a power of 80%. SAS version 9.4 will be used for analysis.

Patients' age, gender, procedure type, and NIDA Quick score will be assessed for their potential as confounding factors. This will support guidance for trial design in Phase II.

The study sample of this pilot is likely underpowered to perform meaningful subanalyses of differences in intervention effect between gender and racial/ethnic subgroups. They will be performed to not miss potentially clinically significant differences as prescribed by NIH policy.

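### The 7-day drug-use comparison makes no use of the medications recorded at baseline, which costs precision in one secondary outcome

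*Combined protocol and SAP*

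**What the plan says.** Section 6.2.2 (Baseline Assessments) lists medical history and medications among the items that "will be recorded on the Tufts University School of Dental Medicine Research Participant& Dental History form (Appendix"). Section 6.2.5 has the tablet handed over after the baseline data are obtained, so the medication list is a pre-intervention measurement.

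Section 9.5.2 makes "use of prescription and nonprescription drugs for 7 days after treatment" a secondary outcome. It is not restricted to drugs started after the visit.

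Section 9.6 gives the test: "Drug usage, converted in equivalence drug score, and satisfaction scores will be assessed by t-test if normally distributed or Mann-Whitney-U test if non-normal". No baseline term, change score or stratification is mentioned. The same section says that "Patients' age, gender, procedure type, and NIDA Quick score will be assessed for their potential as confounding factors"; baseline medication is not on that list.

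The only baseline-to-diary drug comparison is in section 6.2.2: "The information collected via the NIDA quick screen will be compared to post-visit self-reported medication data from the diary". That section describes the screen as covering tobacco, alcohol, illegal substances and "nonmedical use of prescription drugs".

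Patients qualify if "Scheduled to undergo a dental procedure at the Craniofacial Pain Center" (section 4.1). Section 4.2 has no exclusion for existing analgesic, opioid or sedative use, and section 5.3.3 (Prohibited Interventions) is marked not applicable.

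**The concern.** Some patients attending a pain clinic can be expected to take analgesics, opioids or sedatives already, and nothing in the plan keeps them out. What they go on taking after the visit enters the 7-day score in full. To the extent that this reflects earlier use, it adds variation unrelated to the app. With about 38 diaries, the number of existing users can also differ noticeably between arms by chance.

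The plan already takes baseline into account elsewhere: section 9.6 compares waiting-room anxiety and pain as change from start to end. Drug use gets no comparable treatment, although a baseline list is collected. At stake is how well the pilot can describe one of the stated Phase II hypotheses in section 9.1, less need for opioids and analgesics in the week after treatment.

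**Working it through.** **Inputs from the documents.** 38 diary packages expected from 72 patients, 1:1 allocation, two-sided alpha 0.05 (sections 9.1, 9.2, 9.6). An equal split gives 19 diaries per arm.

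**Inputs assumed, because the documents do not give them.**
- Correlation r between baseline use and the 7-day score: 0.3 to 0.7.
- Illustrative app effect: 0.6 SD.
- Proportion of existing users: 10% to 50%.

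**Step 1: the plan's own figure.** No sample size is given for drug use. The 38 in section 9.2 is for diary pain: difference 3.5 − 1.6 = 1.9, SD 2.0, power 0.80. The normal approximation gives 2 × (1.960 + 0.842)² × (2.0/1.9)² = 17.4, so 18 per arm (36 in total). The t-distribution gives 18.4, so 19 per arm and 38 in total. The stated 38 reproduces, and this point does not dispute it.

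**Step 2: gain from adjustment.** With a linear baseline covariate, the residual variance is (1 − r²) times the unadjusted variance. The effective number of diaries is 38/(1 − r²), and the standardised effect becomes 0.6/√(1 − r²). Power is from the non-central t with 19 per arm.

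| r | variance removed | effective diaries | standardised effect | power |
|---|---|---|---|---|
| unadjusted | 0% | 38 | 0.60 | 0.44 |
| 0.3 | 9% | 41.8 | 0.63 | 0.47 |
| 0.5 | 25% | 50.7 | 0.69 | 0.55 |
| 0.7 | 49% | 74.5 | 0.84 | 0.71 |

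Losing one to three degrees of freedom lowers these powers by about 0.002 at most. The figures assume a linear covariate and a roughly normal outcome. No gain was computed for a yes/no covariate, a stratified Wilcoxon test or rank ANCOVA; reducing baseline use to yes/no loses information, so its gain would be smaller.

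**Step 3: chance imbalance in existing users.** Let X and Y be independent Binomial(19, p) counts of existing users in the two arms. A gap of 4 users is 4/19 = 21 percentage points.

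| assumed p | P(gap of at least 4) |
|---|---|
| 10% | 6% |
| 20% | 15% |
| 30% | 21% |
| 40% | 25% |
| 50% | 26% |

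**Step 4: what an imbalance does to the estimate.** On a continuous baseline score, the standardised difference between arms has standard error √(2/19) = 0.32. A difference above 0.5 SD in either direction has probability about 12% (normal approximation). It would move the unadjusted drug-use difference by r × 0.5, which is 0.15 SD at r = 0.3 and 0.35 SD at r = 0.7.

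**The case against.** **The unadjusted test is valid.** A reader might infer that an imbalance in existing users makes the comparison biased, or creates false app effects beyond the nominal rate. Under 1:1 randomisation it does neither: chance imbalance in a prognostic factor is already covered by the type I error of the unadjusted test. This stands, and it limits the complaint to precision and to how far one trial's estimate can move.

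**The extent of existing use is unknown.** A reader might also infer that earlier use dominates the 7-day score. The documents give neither a prevalence nor a correlation, and the précis (Sample Size and Population) describes a mixed clinic that fits bite and sleep-apnea appliances as well as giving nerve blocks. Even at r = 0.7, baseline use explains 49% of the variance, which is less than half; at r = 0.3 the gain in power is only 0.03.

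**The plan is provisional.** Section 9.6 says that the approach may change with the Phase I data and that the confounder assessment will guide Phase II design. This softens the point. It does not remove it, because baseline medication is not among the factors to be assessed.

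**NIDA covers prior drug use.** It does so only in part. By the protocol's own description it measures substance use and nonmedical prescription use, so it cannot stand in for drugs taken as directed. Assessing it as a possible confounder also does not commit the plan to an adjusted comparison.

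**The form may lack dose.** The history form is an appendix that is not shown, so its detail is unknown. A yes/no covariate remains possible, with a smaller gain.

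**Conclusion.** The point holds as a matter of precision in one secondary outcome. A relevant baseline measurement is collected and then left out of both the drug-use comparison and the list of factors to assess, and the NIDA score does not replace it. Under the assumptions above, adjustment removes 9% to 49% of the variance and raises power for a 0.6 SD effect from 0.44 to between 0.47 and 0.71. The size depends on a correlation that the documents do not give, and on a covariate recorded in more detail than yes/no. The chance of a gap of at least 4 existing users runs from 6% to 26%, depending on the assumed prevalence.

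A reader might go further and conclude that Phase II would be mis-sized. The documents do not support that: the Phase II primary outcome is waiting-room anxiety, and section 9.2 sizes nothing on drug use. What Phase I would lose is information for planning the Phase II drug-use analysis. The Phase I primary outcome, complete on-site data sets, is unaffected.

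**What to change.** In section 9.6:

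1. Compare the 7-day drug score with a model containing arm and baseline use of the same drug class, taken from the section 6.2.2 medication list. If dose is not recorded, use yes/no indicators for regular use of opioids, other analgesics and sedatives.
2. If the score is skewed, replace the plain Mann-Whitney test with a van Elteren (stratified Wilcoxon) test by baseline use, or with rank ANCOVA.
3. Add baseline medication to age, gender, procedure type and NIDA score as a factor to be assessed.
4. Report the adjusted SD and the baseline-to-diary association as information for the Phase II drug-use analysis. Note that section 9.6 already allows the plan to be adapted and that the Phase II primary outcome is waiting-room anxiety.

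The cost is a few lines of analysis text, coding of a list that is already collected, and one to three degrees of freedom. It adds no procedure and no burden on participants.

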#### Randomization

Randomization will be performed after completion of screening and baseline to determine which tablet and thereby study intervention the patient will receive.

#### 6.2.3 Blinding

Treating dental personnel will be blinded to group attribution. The treating personnel are the subject's regular scheduled providers, and are not part of the study team. The four tablets used in the study will be labeled A,B,C,D and will be preloaded with the app or white noise by the Hypnalgesics, LLC in randomized sequence. The study personnel at TUSDM will not be aware which tablet presents test or control content. The opening screen and option screen of the white noise control app will use the same color scheme and lay-out as the one of the test Comfort Talk app to minimize the likelihood that personnel become aware of the patient's group attribution. While there may still be a possibility of unblinding in the waiting room or procedure room should the patient ask the research assistant a direct question, strict blinding will be maintained for the analysis for the data. The statistical team of [name] and [name] will receive the encoded data entries and will not be informed about the content of the tablets until all analyses are completed. Since they also will not have direct contact with the study patients they are also not at risk of becoming unblinded during app use by the patients.

Patients randomized to the app will receive a download coupon for the app at the time of their visit for home use. Patients attributed to the control group will receive a coupon code after their return their post-visit diary a week later. To enable this while maintaining blinding of study personnel, at the end of their visit, all patients will receive a sealed envelope exteriorly labeled with A,B,C,D according to their group attribution. The Hypnalgesics, LLC will have prefilled and sealed the envelopes according to group attribution either with a download coupon for patients receiving the test tablets, and a thank you note and information that they will receive their download code after they send in their questionnaire for control patients.

All patients sending back their diaries will receive the download coupon with their check. This will lead to some duplication for the test patients who already had received a download coupon at the time of their clinic visit but this will maintain blinding of study personnel.

The study intervention does not carry risks such as drug trial would in that patient management would need be changed based on which group a patient had been attributed to. Therefore circumstances which would require breaking the bind are not envisioned.

